4 STUDY DESIGN

This protocol is a single site study. The study will include a baseline 3T MRI session, and two experiments conducted during two sessions of simultaneous TMS, EEG, and cognitive testing (Figure 1). Both experiments will use the same participants to allow for within-subjects comparisons and the order of experiments will be counterbalanced. Participants who miss a session will be rescheduled or replaced (see Recruitment). Participants will make three visits to the lab, a baseline assessment session and two TMS/EEG sessions, for a time commitment of approximately 8 hours. TMS/EEG Session 1 will occur 1-31 days following the baseline visit and TMS/EEG Session 2 will occur 4-31 days following TMS/EEG Session 1 (Figure 1).

Figure 1. Study Design

[figure not shown]
On each TMS/EEG day, participants will undergo EEG recording using a 64-channel elastic cap. During recording, they will complete two blocks of a task, one for each experiment, which differ only in their timing of TMS delivery. Each block consists of 90 study trials of episodic memory encoding (45 trials) and spatial processing (45 trials) for a total of 180 trials (90 memory and 90 spatial processing) per TMS/EEG session (Table 1).

Table 1. Conditions and trial counts.

	Parietal Stimulation				Vertex Stimulation				TOTAL			
	Stim On		Stim Off		Stim On		Stim Off					
	Memory	Spatial	Memory	Spatial	Memory	Spatial	Memory	Spatial				
Experiment 1	30	30	15	15	30	30	15	15	180	360		
Experiment 2	30	30	15	15	30	30	15	15	180			

TMS will be paired with task trials and consist of 2-second trains of continuous theta burst stimulation (cTBS; see Study Procedures). In Experiment 1, TMS will be delivered during the rest phase immediately prior to trial onsets (Figure 2). In Experiment 2, TMS pulses will occur during the trial while participants are actively engaged in the task (Figure 2). The order of experiments will be counterbalanced across subjects within each session. TMS will be delivered to an episodic memory network-connected location in posterior parietal cortex (see 4.4.2. TMS, below) or to the vertex as an inactive control condition, and the order of stimulation location will be counterbalanced across TMS/EEG sessions. One-third of trials will contain no stimulation as an additional control to examine behavioral and neural effects in the absence of the TMS sensory artifact (Table 1). Participants will then be tested on encoded items, also with EEG recording. EEG data will be examined in an event-related design, with timeseries following trial onsets compared across task (memory encoding, spatial processing, and memory retrieval) and stimulation (parietal-TMS, vertex-TMS, and no-TMS) conditions.

Figure 2. Experiment Design

Recruitment

Healthy participants will be recruited from the pool of individuals self-referring to the study directly and via the NIH Clinical Research Volunteer Program and via advertisements that will be pre-approved by the IRB. Although NIH employees will be allowed to participate, no direct solicitation of employees/staff by supervisors or co-workers will take place. Any recruitment material will be IRB approved. Participants who indicate interest will be pre-screened by phone. Pre-screening questions are listed in Appendix B. IRB-approved ads will be posted on NIH listservs with the permission of the moderator and IRB required statement on how the receiver was identified. Listservs may include NIH sponsored recruitment list serves such as (NIH HV recruitment list serv). Listserv announcement will include:

“You are receiving this message because your email address is included in the above NIH Listserv mailing list. The purpose of this message is to inform you of studies that are recruiting

Abbreviated Title: Task-dependent TMS and memory

Version Date: 11.15.22

volunteers at NIH, Bethesda, Maryland. The moderator of the listserv mailing list has permitted its use for this distribution”.

It is possible that some participants will miss a session. If this occurs, and the participant is still willing to participate, we will reschedule. If a participant no longer wishes to continue with the study, a new participant will be recruited for the full study. If they have data from one experiment, those data will still be included in analysis for that experiment but excluded from any comparisons across experiments.

It is possible that technical problems may arise. If this occurs, and the participant is willing to continue with the study, we will reschedule.

Screening

Participants who pass pre-screening will be invited to participate in the study and scheduled for consent and formal screening.

Upon arrival to the screening appointment, written, informed consent will be obtained by an investigator and formal screening will be done according to Appendix A.

Volunteers who have not had a neurological exam from an NINDS provider within the past two years will receive a neurological examination from an NINDS physician or nurse practitioner. This will not replace any exam the participant will receive for purposes of medical care; the exam will be for research purposes only. All women of child-bearing potential will have a urine pregnancy test (not earlier than 24 hours) before each MRI scan.

In some cases, consent, screening, and examination (when required) may be performed on the same day as the baseline MRI.

Study procedures:

Behavioral Tasks

Memory Task: This is a test of episodic memory, including item recognition and context recollection^{30,52,53}. In the task, participants will be shown a series of objects in one of four quadrants on the screen. They will be instructed to remember the objects and where they were located, both of which will be tested later. To ensure attention and for consistency with the spatial task (see below), they will be asked to indicate by button press whether the object is primarily used outdoors (e.g., a baseball) or indoors (e.g., a television). During the encoding phase, each object will be presented for 4 seconds with 4 seconds between trials. In Experiment 1, TMS will occur during a 2 second cue before each trial and in Experiment 2, TMS will occur in the first 2 seconds of stimulus object presentation. There will be 180 encoding trials, interspersed with 180 trials of the spatial task (described below). Trial order will be randomized. The retrieval phase will occur following the end of encoding. Participants will be shown, sequentially and in randomized order, the 180 encoded objects and 180 new lure objects, for a total of 360 trials. For all trials, they will respond with whether the object was old (previously seen) or new (not previously seen) and their confidence on a scale of 1-6 (1=confident new,

Abbreviated Title: Task-dependent TMS and memory

Version Date: 11.15.22

6=confident old) as a measure of item recognition. If the object was previously seen, participants will then be asked which quadrant the item was presented in to provide a measure of context recollection. We will use two different versions of the task with different and non-overlapping sets of objects at the two test sessions and the order of versions will be counterbalanced across participants.

Spatial Task: This is a test of spatial processing, which will serve as a control task to isolate neural markers of memory engagement, versus engagement in any task with similar visuospatial qualities. Notably, spatial processing activates a network of frontoparietal including the posterior parietal cortex regions^{54,55}, allowing it to further serve as a control to isolate hippocampal network effects of TMS from the local effects of TMS on the stimulated region. In each trial of this task, participants will be shown an arrow pointing to one corner of the screen and displayed in one of four quadrants. They will be instructed to indicate by button press whether the arrow points to the corner in which it is displayed (“match,” e.g. pointing to the upper right corner in the upper right quadrant) or a different corner (“no-match,” e.g. pointing to the upper right corner in the upper left quadrant). Accuracy of match/no-match responses will be assessed. Each arrow will be presented for 4 seconds with 4 seconds between trials. In Experiment 1, TMS will occur during a 2 second cue before each trial and in Experiment 2, TMS will occur in the first 2 seconds of stimulus presentation. There will be 180 trials, interspersed with encoding trials of the memory task. We will use two different versions of the task at the two test sessions.

TMS

The parietal target will be the region of the left posterior parietal cortex with the greatest connectivity with the left hippocampus derived from the baseline resting-state fMRI session³¹. This region was chosen because of its dense connections with the hippocampus^{56,57}. Thus, stimulation of this location can modulate function of the hippocampal-cortical network^{30-36,38}.

The control target will be vertex, a commonly used active control site which does not influence neural or behavioral activity⁵⁸.

TMS targets will be marked in the participant’s anatomical MRI volume and located with a frameless stereotaxic system. If any experiment, for any reason, fails to produce useful individual targets, a literature-based location for the parietal cortex³¹ will be used as our location of stimulation. To reduce the influence of diurnal variations in the responsiveness to neuroplasticity protocols⁵⁹, we will make every effort to test subjects during the same time of day.

[figure not shown]
Stimulation will be delivered during the encoding phase of the behavioral task, either prior to trial onset (Experiment 1) or simultaneously with trial onset (Experiment 2; see 4.4.1 Behavioral Tasks for timing) in the form of 2-seconds of theta-burst stimulation (50 Hz pulse triplets every 200 ms; Figure 3) at 80% of the motor evoked potential threshold of the right abductor pollicis brevis muscle or 44% of maximum stimulator output, whichever is lower. This protocol has been

Abbreviated Title: Task-dependent TMS and memory

Version Date: 11.15.22

shown previously to particularly influence the hippocampal-cortical network and memory performance³⁷⁻³⁹.

Figure 3. Theta-burst stimulation.

EEG

Participants will be fitted with a 64-channel elastic EEG cap for the duration of each experiment session. Data will be recorded continuously during the study and test phases of the behavioral experiment. The EEG signal will be amplified online, filtered, and digitized continuously along with stimulus onset codes used for subsequent analysis. Independent component analysis and/or other processing techniques will be performed to isolate and remove recurring artifacts from the signal.

Single-trial waveforms will be screened for artifactual contamination. Trials will then be divided based on task type (spatial, memory encoding, accuracy of item recall (memory task) and spatial task performance. The timeseries from trials of the same type and/or accuracy will then be averaged, and the resulting waveforms will be compared across categories. For theta/alpha band analysis, we will additionally use time-frequency decomposition of the event-related averages.

MRI

We estimate a maximum of 1 hour for baseline scanning. Because scanner malfunctions and subsequent loss of data are common, we will not report these as unexpected problems.

Participants whose data are lost due to scanner malfunctions will be rescheduled, if possible.

Participants whose MRI sessions cannot be completed may enter the experiment if the MPRAGE (see below) data have been acquired. They will be rescheduled for the other scans when possible.

MRI anatomical scanning: All participants will have anatomical (MPRAGE) scans at baseline. Participants who have not had one in the past year will receive a standard clinical MRI scan of the head, which will be submitted to the Diagnostic Radiology Department CC for interpretation. Depending on the requirement for a clinical scan, this phase will take 10-30 min.

Abbreviated Title: Task-dependent TMS and memory

Version Date: 11.15.22

Resting-state scanning: All participants will receive a resting-state fMRI scan at baseline for identification of a TMS target. During scanning, participants will be instructed to lie motionless with open eyes fixated on a cross that is presented on a screen visible through a mirror attached to the MR head coil (approximately 10 min).

Diffusion-weighted scanning: Participants will have a diffusion-weighted scan for diffusion tensor imaging (DTI) scanning at baseline to estimate white matter structural connectivity. This phase will take approximately 20 min. This may be omitted in some cases due to time constraints.

Justifications for MRI and TMS non-significant risk (NSR) designation

Research Pulse Sequences:

a. These custom sequences all operate under the International Electrotechnical Commission (IEC) 60601-2-33, First Level-Controlled Operating Mode. The IEC/FDA set operating mode limits on the MRI for RF heating (Specific Absorption Rate) and Time-varying magnetic field gradients (dB/dt) that are fully operational for all research pulse sequences. This device has not received pre-market approval or 510 (K) clearance by the FDA.

MRI Research Analysis and Reconstruction Software:

a. This software conforms to operate under the International Electrotechnical Commission (IEC) 60601-2-33, First Level-Controlled Operating Mode. The IEC/FDA set operating mode limits on the MRI for RF heating (Specific Absorption Rate) and Time-varying magnetic field gradients (dB/dt) that are fully operational for all research pulse sequences. This device has not received pre-market approval or 510 (K) clearance by the FDA.

Magstim Rapid2 with Air Film coil TMS (Magstim):

a. This device is classified as an FDA cleared device with 510(K) clearance by the FDA #K143531, K162935. The indicated use according to the 510(K) is the treatment of Major Depressive Disorder in adult patients who have failed to achieve satisfactory improvement from prior antidepressant medication in the current episode. In this study, this device is intended to be used to investigate how TMS modulates EEG neural measures of successful memory and the association of this modulation with behavioral performance, and not for diagnostic purposes. Therefore, it does not conform to the 510(k) label.

BrainVision actiCHamp Plus EEG (Brain Vision):

a. The Sponsor has confirmed with the manufacturer that there is no market clearance or approval for this device in the US and that the device does not meet criteria for exemption under 21CFR812. This device has not received pre-market approval or 510 (K) clearance by the FDA.

According to 21 CFR 812.3 (m) and FDA “Information Sheet Guidance for IRBs, Clinical Investigators, and Sponsors: Significant Risk and Nonsignificant Risk and Nonsignificant Risk Medical Device Studies January 2006 (accessible at: <http://www.fda.gov/downloads/RegulatoryInformation/Guidances/UCM126418.pdf>) the use of

Abbreviated Title: Task-dependent TMS and memory

Version Date: 11.15.22

these devices in the study are a Non-significant Risk study. 21 CFR 812.3(m) enumerates four criteria for a Significant Risk Device Study; none of these apply to this study:

1. is intended as an implant and presents a potential for serious risk to the health, safety, or welfare of a subject;

No. All devices listed in this section are not intended as implants and do not present a potential for serious risk to the health, safety, and welfare of a subject

2. is purported or represented to be for a use in supporting or sustaining human life and presents a potential for serious risk to the health, safety, or welfare of a subject;

No. All devices listed in this section are not purported or represented to be for

3. *a use in supporting or sustaining human life and presents no potential for serious risk to the health, safety, or welfare of a subject.* is for a use of substantial importance in diagnosing, curing, mitigating, or treating disease, or otherwise preventing impairment of human health and presents a potential for serious risk to the health, safety, or welfare of a subject; or

No. All devices listed in this section are not intended for use of substantial importance in diagnosing, curing mitigating, or treating disease, or otherwise preventing impairment of human health and presents no potential for serious risk to the health, safety, or welfare of a subject.

4. otherwise presents a potential for serious risk to the health, safety or welfare of a subject

No. All devices listed in this section do not present a potential for serious risk to the health, safety, or welfare of subjects.

The protocol will comply with the abbreviated IDE requirements under 21 CFR 812.2(b), available at:

<https://www.accessdata.fda.gov/scripts/cdrh/cfdocs/cfCFR/CFRSearch.cfm?fr=812.2>

Devices determined to be used on label or other exempted devices pursuant to 21CFR812.2(c):

GE Discovery MR 750 System-3T. 510k: K163331

- a. This device and associated system carries an FDA 510(k) clearance . The Sponsor has determined that the device is used in the trial in accordance with this label.

Primary Objective

Primary Objective 1: Investigate how TMS modulates EEG neural measures of successful memory and the association of this modulation with behavioral performance

- Hypotheses

Abbreviated Title: Task-dependent TMS and memory

Version Date: 11.15.22

- Network-targeted parietal-TMS will improve memory performance (context recollection; Primary Outcome Measure 1) on parietal-TMS relative to vertex-TMS trials
- Relative to vertex-TMS, parietal-TMS will also increase the Late Positive Posterior ERP (Primary Outcome Measure 2) and theta power (Secondary Outcome Measure 1) during encoding on successful trials, relative to unsuccessful trials
- The EEG effects will correlate with memory improvement (Correlation, Primary Outcome Measure 1 and Primary Outcome Measure 2/Secondary Outcome Measure 1)
- Additionally, parietal-TMS will alter EEG functional connectivity patterns (Exploratory Outcome Measure 1) at encoding during successful trials relative to unsuccessful trials
- Parietal-TMS will not influence neural activity or accuracy for spatial trials, relative to vertex-TMS and no-TMS

Primary Objective 2: Examine how memory task state influences susceptibility to plasticity via TMS and determine the optimal neural state for improving memory

- Hypotheses
 - Network-targeted parietal-TMS during memory encoding will have a larger effect on source recollection (Primary Outcome Measure 1), relative to pre-trial parietal-TMS and vertex-TMS during encoding
 - Exploratory Analyses:
 - Parietal-TMS during memory encoding will increase the Late Positive Posterior ERP (Primary Outcome Measure 2) and theta-power (Secondary Outcome Measure 1), relative to pre-trial parietal-TMS and vertex-TMS during encoding
 - Additionally, parietal-TMS will alter EEG functional connectivity patterns (Exploratory Outcome Measure 1) during later-remembered trials, relative to pre-trial parietal-TMS and vertex-TMS during encoding
 - Network-targeted TMS will not influence neural activity during arithmetic trials, relative to vertex-TMS and no-TMS

Exploratory Objective:

Search for MRI predictors of the effects of parietal TMS

- Measurement of baseline resting-state functional connectivity (Exploratory Outcome Measure 3) and fractional anisotropy (Exploratory Outcome Measure 4) between the hippocampus and cortical regions of the episodic memory network, particularly the precuneus⁶⁰, and look for correlations with the effects of TMS on memory and task-related EEG events across participants.

End of participation

Participants will remain under the care of their own providers. No care will be offered to those participating in this protocol, except for any acute care required for adverse events. Findings of

clinical significance, e.g., significant pathology on MRI will be shared with participants and any provider whom they designate.

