8.3.2 Analysis of the Primary Endpoints

- Primary Endpoint 1: Investigate how TMS modulates EEG neural measures of successful memory and the relevance of modulation to behavioral performance
This aim will examine behavioral and EEG neural outcome measures (Primary Endpoints 1-4). We will perform 3x3 ANOVAs on each outcome measure with the factors trial type (successful/ unsuccessful/ spatial), stimulation site (parietal/ vertex/ none), and their interaction. We will particularly focus on the main effect of stimulation site to determine

the influence of parietal-TMS on memory performance and its neural correlates, and the interaction effect to determine the task specificity of TMS effects. Thresholds for significant effects will be set at $p<0.025$ following FDR correction for multiple comparisons.

- Primary Endpoint 2: Examine how memory task state influences susceptibility to plasticity via TMS and determine the optimal neural state for improving memory
This aim will examine behavioral and EEG neural outcome measures (Primary Endpoints 1-4). We will perform 3x3x2 ANOVAs on each outcome measure with the factors trial type (successful/ unsuccessful/ spatial), stimulation site (parietal/ vertex/ none), stimulation timing (pre-trial and mid-trial) and their interaction. We will particularly focus on the interaction effect of stimulation site and timing to determine the influence of memory task-state parietal-TMS on memory performance and its neural correlates, and the three-way interaction effect to determine the task specificity of state-dependent TMS effects. Thresholds for significant effects will be set at $p<0.025$ following FDR correction for multiple comparisons.

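### Both stimulation timings share one session and site, so unequal carry-over between blocks can bias the Objective 2 site-by-timing contrast in either direction, and the model has no experiment-order term

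*Combined protocol and SAP*

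**What the plan says.** Section 4 (Study Design) states that on each TMS/EEG day "they will complete two blocks of a task, one for each experiment, which differ only in their timing of TMS delivery". Experiment 1 is pre-trial stimulation and Experiment 2 is mid-trial. The stimulation site is fixed within a day: "the order of stimulation location will be counterbalanced across TMS/EEG sessions". The two days are well separated: "TMS/EEG Session 2 will occur 4-31 days following TMS/EEG Session 1". For the two timings within a day the only stated control is "The order of experiments will be counterbalanced across subjects within each session".

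Under Primary Objective 2, Section 4 predicts that "Network-targeted parietal-TMS during memory encoding will have a larger effect on source recollection", compared with pre-trial parietal and with mid-trial vertex stimulation. Section 8.3.2 tests this in a 3x3x2 ANOVA with trial type, site (parietal, vertex, none) and timing: "We will particularly focus on the interaction effect of stimulation site and timing". The model contains no block position, experiment order or carry-over term, and no sensitivity analysis for order is planned.

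The layout of a session is only partly described. Trial spacing is given ("each object will be presented for 4 seconds with 4 seconds between trials"), and "The retrieval phase will occur following the end of encoding", but the text does not say whether retrieval follows each block or both.

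**The concern.** The timing comparison is a two-period crossover inside one session. The second block follows a full block of stimulation to the same target on the same day, with no stated washout, whereas the two sites are at least four days apart. Section 2.2 gives reason to expect either pattern: it reports that single sessions of theta-burst stimulation affect memory, and also that time-locked trains act trial by trial. Carry-over between blocks is therefore plausible but not established.

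The site-by-timing interaction is the main test of Objective 2, which seeks the optimal neural state for improving memory. If carry-over differs by timing, neither a null nor a positive interaction can be read at face value, and the planned analysis gives no clear sign of it. A second, independent issue is that the order rule does not say whether a participant keeps the same experiment order in both sessions. That decides whether ordinary first-versus-second-block shifts (fatigue, practice, retention interval) cancel from the contrast.

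**Working it through.** **Inputs from the documents.** Table 1: 30 memory and 30 spatial stim-on trials per block, so 60 trains; 15 stim-off memory trials per block. Section 4 (TMS): 2-second trains with a triplet every 200 ms, so 10 x 3 = 30 pulses per train and 60 x 30 = 1,800 pulses before the second block starts. Section 8.2: 32 complete participants, power 0.80, alpha 0.025 per outcome, eta-squared 0.44 and 0.28. **Assumed:** k, the carry-over as a share of the direct effect, shown over a range.

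**1. The plan's own figure.** With f² = 0.28/0.72 = 0.389, noncentrality N·f², df 2 and 2(N-1), and alpha 0.025, power is 0.793 at N = 31 and 0.809 at N = 32. So 32 reproduces under this setting. The documents do not give the number of measurements, their correlation or a sphericity correction, so other settings are possible.

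**2. Bias.** Let P and M be the parietal-minus-vertex effects pre-trial and mid-trial, and let L_pre and L_mid be what each leaves in the following block. Vertex is taken as inactive, as Section 4 does.
- Pre-trial first: contrast = M + L_pre - P
- Mid-trial first: contrast = M - P - L_mid
- Mean over orders: (M - P) - (L_mid - L_pre)/2

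Simulation with M = 1, P = 0.4 (true contrast 0.60), 32 participants and 20,000 replicates:

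| Carry-over | L_mid | L_pre | Estimated contrast |
|---|---|---|---|
| none | 0 | 0 | 0.60 |
| equal | 0.3 | 0.3 | 0.60 |
| proportional, k = 0.5 | 0.5 | 0.2 | 0.45 |
| proportional, k = 1 | 1.0 | 0.4 | 0.30 |
| larger after pre-trial | 0.2 | 0.5 | 0.75 |
| opposite sign, k = -0.5 | -0.5 | -0.2 | 0.75 |

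With M = P = 0.7, L_mid = 0.5 and L_pre = 0.2, the contrast is -0.15: a difference where none exists.

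**3. Size under proportional carry-over (L = k x direct effect).** Parietal minus vertex keeps 1 - k/2. The planned test has three site levels, with none pooled over both days. Additive carry-over also shifts the parietal-day stim-off trials, which are half of that pool. With D = M - P, the mid-minus-pre differences are D(1 - k/2) for parietal, 0 for vertex and -kD/4 for none. Assuming equal variances, the interaction sum of squares relative to k = 0 is R = [(1 - k/2)² + (k/4)² - (1 - 3k/4)²/3] / (2/3).

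| k | Two-level contrast kept | Sample-size factor 1/(1 - k/2)² | R, three-level | Factor 1/R | Power at N = 32, f² = 0.389·R |
|---|---|---|---|---|---|
| 0 | 1.000 | 1.00 | 1.000 | 1.00 | 0.81 |
| 0.25 | 0.875 | 1.31 | 0.824 | 1.21 | 0.71 |
| 0.5 | 0.750 | 1.78 | 0.672 | 1.49 | 0.61 |
| 1 | 0.500 | 4.00 | 0.4375 | 2.29 | 0.40 |

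The power column is illustrative: the 0.28 comes from a study of pre-trial stimulation, not of a timing contrast.

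**4. Block shift.** Add b to everything in the second block. The participant's contrast is (parietal mid - parietal pre) - (vertex mid - vertex pre). Same order on both days: b - b = 0, or -b + b = 0. Different orders: b - (-b) = 2b, or -2b. Each such participant's contrast gains variance 4b². With balanced orders this is noise, not bias.

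**5. What a first-block comparison costs.** Let s² be the variance of a one-block parietal-minus-vertex difference and r its correlation between blocks. With 16 versus 16 participants the variance is 2s²/16; pooled, it is 2s²(1 - r)/32. The ratio is 2/(1 - r), so the standard error is 1.41 times larger at r = 0 and 2.0 times at r = 0.5.

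**The case against.** The strongest reply is that the direction is unknown. A reader might infer that the contrast is pulled toward zero precisely when Objective 2's hypothesis is true. The documents do not support that. The hypothesis concerns the effect of stimulation during encoding and says nothing about residue. Attenuation needs carry-over that exists, has the same sign as the direct effect and is larger after mid-trial stimulation. The Objective 2 language about susceptibility to plasticity makes this a natural case, but the trial-by-trial evidence in Section 2.2 points the other way. This part of the reply stands.

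Second, every block contains stim-off trials, and none is a level of the site factor. For the planned three-level test the loss is therefore smaller than parietal minus vertex alone suggests (1.49 rather than 1.78 at k = 0.5), and a within-session on-minus-off contrast has no loss when carry-over shifts on and off trials equally. That also stands. The plan does not specify such a contrast, however, and pooling none across days dilutes the signal it could give.

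Third, a reader might take the blocks to be back to back. The text does not say so: retrieval may separate them, and Figures 1 and 2, which could show an interval, are not readable in the available text. What is explicit is same day, same site and no interval stated in the readable text.

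Fourth, nothing says that a participant's two orders differ, and no value of b is given. True, but nothing says they match either, and matching them is almost free.

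**Conclusion.** The concern holds in conditional form. The site-by-timing contrast may be biased by half the difference in carry-over between timings; neither the size nor the sign can be derived from the documents. Under positive proportional carry-over with k up to 1, up to half of the parietal-minus-vertex contrast is lost and its sign does not change. Carry-over that is larger after pre-trial stimulation, or reversed in sign, inflates the contrast. Equal or absent carry-over leaves it unbiased.

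The untied order is a separate, certain gap in the specification. It costs precision rather than validity, by 4b² for each participant whose two orders differ.

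These results assume additive carry-over, an inactive vertex and balanced orders; k and b are not in the documents. The point is worth acting on because it touches Objective 2's main test and the remedy needs no extra visits, participants or stimulation.

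**What to change.** - **Section 4:** give each participant the same experiment order in both TMS/EEG sessions, counterbalanced across participants. State the block layout, including where retrieval falls and any interval between blocks.
- **Section 8.3.2, model:** add experiment order as a between-subject factor with its interactions with site and timing. This does not remove carry-over bias, but makes it visible. Summing over timings, the parietal-minus-vertex effect is M + P + L_pre in one order and M + P + L_mid in the other, so site-by-order estimates the carry-over difference.
- **Section 8.3.2, sensitivity analyses:** (a) a within-session stim-on minus stim-off contrast by site and timing, keeping parietal-day and vertex-day stim-off trials separate, which removes carry-over that shifts on and off trials equally; (b) the first-block-only estimate, comparing parietal minus vertex between participants who began with each experiment, as supportive only.
- **Interpretation:** state that the pooled site-by-timing result, null or positive, assumes equal or no carry-over between blocks.

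**Cost:** one line in the assignment list, some SAP wording and a few error degrees of freedom. Contrast (a) is noisier because each block has only 15 stim-off memory trials. Counting trial noise alone, the parietal-minus-vertex difference of on-minus-off contrasts has variance proportional to 2(1/30 + 1/15) = 0.20, against 2/30 = 0.067 for stim-on trials only, so its standard error is about 1.7 times larger. Estimate (b) has a standard error at least 1.4 times the pooled one, and about 2.0 times at r = 0.5, so it cannot replace the pooled test or settle a null result by itself.
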